### **Diabetes.**

Although the increase in the incidence of post-transplant diabetes mellitus was not significant ( $p=0.359$ ) between Group A (25.6%) and Group B (16.7%), the HbA1c values rose significantly ( $p=0.013$ ) in Group A ( $6.3\pm1.2\%$ ) compared to Group B ( $5.7\pm0.6\%$ ) at the end of the follow-up.

### **Lipid profile.**

No significant differences were noted between the groups in values of total cholesterol ( $164\pm28$  vs  $161\pm27$  mg/dL;  $p=0.677$ ), HDL cholesterol ( $51\pm14$  vs  $44.7\pm10$  mg/dL;  $p=0.095$ ), LDL cholesterol ( $86\pm21$  vs  $92\pm18$  mg/dL;  $p=0.337$ ) or triglycerides ( $140\pm54$  vs  $76\pm9.7$  mg/dL;  $p=0.469$ ) at the end of the follow-up.

### **Blood pressure.**

No significant differences were noted between the groups in diastolic blood pressure values ( $74.9\pm11$  vs  $76\pm9.7$  mmHg;  $p=0.715$ ), although the systolic blood pressure values rose significantly in Group A versus Group B ( $133\pm16$  vs  $125\pm15$  mmHg;  $p=0.055$ ) at the end of the follow-up.

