### *Secondary objectives*

1. To determine the course of the histological findings in the two treatment groups.
2. To determine the course of the balance in the subpopulations of lymphocytes (CXCR3highCD4+/CCR4highCD4+) and regulatory cells (Treg CCR4high) using flow cytometry in samples from peripheral blood and FNAP after withdrawal of steroids in the third month post-transplant versus conventional triple immunosuppression.
3. To analyze and compare the incidence of immunological dysfunction in the two treatment arms, as well as graft and patient survival at one and two years of follow-up.
4. To examine the potential metabolic and cardiovascular benefit of steroid withdrawal in terms of renal function, hypertension, diabetes and hyperlipidemia.
5. To assess the adherence to treatment with immunosuppressors in the two treatment groups and its impact on the generation of DSA.

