#### **FNAP for morphological analysis and flow cytometry:**

The FNAP was done according to the technique of Hayry (Kidney Int. 1989;36:130-141) with the same periodicity as that for the DSA and if there was any suspicion of immune dysfunction. Aspirate samples were obtained with a Ham solution (10 ml). With the 0.8 mm / 25G needle implanted in a Cameco-Gun device the cortical region of the graft was punctured with local anesthesia, and aspirating by vacuum about 20  $\mu$ L of cell material in a Hepes buffer culture

medium with heparin and human serum albumin (Ham solution). At the same time, a blood sample was obtained to calculate the corrected index (CI), which was the result of the differential in the leukocyte count between the FNAP specimen and the peripheral blood sample. The numerical differences for each cell subtype were multiplied by a correction factor and the sum of the different corrected increases described the intensity of the inflammation. A CI greater than 3 was considered suggestive of acute rejection. The aspirate was processed by flow cytometry to analyze the lymphocyte subpopulations in the same way as these were analyzed in peripheral blood, described above.

**Other determinations:** The patients were monitored for renal function, levels of calcineurin inhibitors, blood count and other parameters, and imaging tests as per clinical practice in Spain. The concomitant treatment was also as usual. The fasting glucose figures were monitored daily during the first week, at least twice during the second week, and at least weekly until the end of the first month. During the second and third months they were monitored at least once every two weeks. With effect from the third month and until the end of the first year they were monitored at least once a month. The HbA1c was measured and a standard oral glucose tolerance test of 75 gr was done at 3, 12 and 24 months.

**Pregnancy tests:** These tests were done for all women who were potentially considered to be of child-bearing age in phases I (screening) and II (randomization) of the study. The pregnancy tests were done locally in serum using detection of the human chorionic gonadotropin hormone.

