## **STATISTICAL ANALYSIS PLAN.**

Descriptive statistics are presented together with the various analyses. Both an intention-to-treat analysis and an analysis according to the final treatment were done. The categorical variables were analyzed using the chi-square test or Fisher's exact test, according to needs. The quantitative data were analyzed using the Student t test or the Mann-Whitney U test, according to needs. Changes over time in the DSA and lymphocyte subsets in the two study groups were analyzed using a general linear model for repeated measures, adjusting for confounding variables. Correlations between the various subsets were analyzed using Pearson correlation. The graft and patient survival curves were calculated with the Kaplan-Meier method. The rates of survival of the groups were compared with the log-rank test. Finally, a linear regression analysis was done to determine the factors associated with the generation of de novo DSA, including steroid withdrawal. The data were analyzed using SPSS 20.0.

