### **Histological study of the protocol biopsies**

The results of the protocol biopsies showed that the patients who had subclinical inflammation of the graft at the third month post-transplant had more chronic lesions (p=0.008) and worse renal function than the patients who had no inflammatory lesions. Likewise, the patients who had subclinical tubulo-interstitial inflammation (borderline lesions) 24 months post-transplant had more chronic lesions than those who had no subclinical inflammation (p=0.023) and this was more relevant in those patients who continued to receive prednisone (p=0.020).

The patients with and without subclinical tubulo-interstitial inflammation at the third month post-transplant experienced a significant increase in inflammation (t, i) ( $p<0.001$  and  $p=0.058$ ) and chronic parameters (ct, ci) ( $p=0.017$  and  $p=0.017$ ) at 24 months post-transplant.

Finally, at 24 months post-transplant the increase in acute and chronic lesions ( $p=0.019$  and  $p=0.009$ ) was more relevant in those patients who had borderline lesions at the third month and who ceased steroids.

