### **Renal function.**

No significant differences were noted between the groups in creatinine ( $1.34\pm0.4$  vs  $1.4\pm0.4$  mg/dL;  $p=0.458$ ) or proteinuria ( $209\pm185$  vs  $148\pm82$  mg/24h;  $p=0.303$ ) at the end of the follow-up.

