### **Safety assessment.**

All severe adverse events (SAE) after randomization were monitored and recorded. These SAE were classified according to their nature into three groups: infections of any type (Group A 9.6% vs Group B 22.6%), cardiovascular disease (5.7% vs 3.8%) and neoplasm (3.8% vs 1.9%). No significant differences were seen between the two treatment arms ( $p=0.110$ ,  $p=0.677$ , and  $p=0.618$ ).

There was a tendency in Group B to a higher number of severe infections (urinary sepsis, complicated urinary infections, opportunistic infections, CMV infection) requiring hospitalization. This was possibly because these patients received a higher dose of mycophenolate mofetil at 6 months ( $954\pm162$  vs  $1041\pm211$  mg;  $P=0.08$ ) and 12 months ( $937\pm162$  vs.  $1005\pm174$  mg) after steroid withdrawal. All the infections resolved satisfactorily with the opportune treatment.

Five patients experienced cardiovascular events. Two patients in Group B had ischemic heart disease that was revascularized and three in Group A had ischemic heart disease, ventricular dysfunction and atrial fibrillation, respectively. Finally, three patients developed neoplasms, two skin cancer (basal cell 1 and squamous cell 1) in one patient in each group and one patient in Group A developed cancer in the native kidney.

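### Systolic pressure is called significantly raised at p=0.055 with no n, test, analysis set or alpha given, and the Group B triglyceride entry duplicates diastolic pressure

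*Combined protocol and SAP*

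**What the plan says.** The metabolic and cardiovascular results serve the fourth secondary objective: "To examine the potential metabolic and cardiovascular benefit of steroid withdrawal". They are reported under Preliminary Results.

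- **Blood pressure:** "although the systolic blood pressure values rose significantly in Group A versus Group B", 133±16 vs 125±15 mmHg, p=0.055, at the end of follow-up. Diastolic pressure is 74.9±11 vs 76±9.7 mmHg, p=0.715.
- **Diabetes:** HbA1c is also said to have risen significantly in Group A. Only the end-of-follow-up values are given (6.3±1.2% vs 5.7±0.6%, p=0.013).
- **Lipid profile:** triglycerides are 140±54 vs 76±9.7 mg/dL, p=0.469. HDL is 51±14 vs 44.7±10 mg/dL, p=0.095. Both are called not significant.
- **Histological study of the protocol biopsies:** patients "experienced a significant increase in inflammation (t, i"), with p<0.001 and p=0.058.
- **Renal function:** "No significant differences were noted between the groups in creatinine" or proteinuria, again with means, SDs and p-values only.

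The Statistical Analysis Plan leaves the test open: "The quantitative data were analyzed using the Student t test or the Mann-Whitney U test, according to needs". It also names two analysis sets without ranking them: "Both an intention-to-treat analysis and an analysis according to the final treatment were done". It gives no significance level. The only per-arm denominators are the numbers randomised, 52 (Group A) and 53 (Group B).

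**The concern.** Three things are wrong on the page.

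1. A conclusion of significance is attached to p=0.055, and another apparently to p=0.058, with no stated threshold that would allow it.
2. 'Rose' describes a change, but the Diabetes and Blood pressure sections print no baseline and no change.
3. One Group B entry in the lipid comparison has the same mean and SD as a blood pressure entry.

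Behind these lies a reporting gap. Diabetes, lipids, blood pressure and renal function carry ten between-arm p-values (diabetes incidence, HbA1c, four lipids, two pressures, creatinine, proteinuria). For none of them can the reader tell how many patients were analysed, by which test, or in which analysis set. At stake is whether a blood pressure benefit of steroid withdrawal is read as established, and whether the triglyceride comparison can be read at all.

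**Working it through.** **Inputs.** Means, SDs and p-values come from the results sections named above. The 52 and 53 come from the opening of Preliminary Results. The two-sided 0.05 level is my assumption.

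**1. Labels.** The text calls 0.055 significant, lists 0.058 under a significant increase, and calls 0.095 (HDL) not significant. These labels agree only with an unstated cut-off between 0.058 and 0.095. At two-sided 0.05, 0.055 and 0.058 both miss. The histology sentence covers patients with and without inflammation and two scores (t, i), so it is unclear whether the two p-values belong to the scores or to the patient groups.

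**2. Can p=0.055 be reproduced on all randomised patients?** Pooled t test:

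- Pooled variance = (51×16² + 52×15²)/103 = 24756/103 = 240.35, so the pooled SD is 15.50.
- SE = 15.50×√(1/52 + 1/53) = 3.026.
- t = 8/3.026 = 2.644 on 103 df, **p=0.0095**. The 95% CI is 8 ± 1.983×3.026 = 2.0 to 14.0 mmHg.
- Least favourable rounding (132.5±16.5 vs 125.5±15.5): p=0.027.

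It does not reproduce by t test at 52/53.

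**3. What sizes would give it?**

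- 29 per arm: pooled variance (256 + 225)/2 = 240.5; SE = √(240.5×2/29) = 4.073; t = 1.964 on 56 df; p=0.0545; 95% CI 8 ± 2.003×4.073 = −0.2 to 16.2 mmHg. Allowing for rounding, equal arms of 22 to 39 fit.
- 19 and 53: pooled variance (18×256 + 52×225)/70 = 232.97; SE = 15.26×√(1/19 + 1/53) = 4.081; t = 1.960 on 70 df; p=0.054, which fits within rounding.

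The p-value therefore does not fix the number analysed. HDL behaves similarly: p=0.009 at 52/53 against the printed 0.095, which fits about 22 per arm if arms are equal.

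**4. Triglycerides.** At 52/53 the pooled SD is 38.62, SE 7.538 and t = 64/7.538 = 8.49, so p is about 2×10⁻¹³. Searching every pair of sizes from 2 to 52 and 2 to 53, by Student and Welch, the largest p is 0.342 (Welch, 2 and 53). With at least 10 in each arm it is 0.005. The printed 0.469 is out of reach. The same 76±9.7 in the diastolic row gives p=0.715 at 24 per arm, exactly as printed, so those figures fit diastolic pressure and not the triglyceride row.

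**5. Do denominators vary?**

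- Safety assessment: "infections of any type (Group A 9.6% vs Group B 22.6%), cardiovascular disease (5.7% vs 3.8%) and neoplasm (3.8% vs 1.9"). Counts of 5, 3 and 2 out of 52 and 12, 2 and 1 out of 53 give 9.6% vs 22.6%, 5.77% vs 3.8% and 3.8% vs 1.9%. Fisher p-values are 0.110, 0.678 and 0.618, against the printed 0.110, 0.677 and 0.618. The match to the full arms is complete except for one unit in the last digit in two places (5.7% and 0.677).
- Acute rejection: 7.14% in Group A fits only 1/14, 2/28 or 3/42; out of 52, the neighbours are 3/52 = 5.77% and 4/52 = 7.69%. In Group B, 11.54% fits only 3/26 or 6/52; out of 53, the neighbours are 6/53 = 11.32% and 7/53 = 13.21%.

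So safety uses the full arms and rejection does not, without any statement to that effect.

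**The case against.** **The p-values may be correct.** The plan permits a Mann-Whitney test and a second analysis set, and the results are headed preliminary, so follow-up may be unfinished. This stands. A reader might infer from step 2 that 0.055 is a miscalculation; the documents do not support that. A rank test cannot be checked from means and SDs. A Mann-Whitney test on both full arms is an unlikely explanation: in 4,000 simulated data sets with the printed means and SDs, normal or lognormal, about 0.1% gave p of 0.0545 or more. A subset remains entirely possible.

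**Relabelling could bury a real difference.** This also stands. It would be tempting to declare systolic pressure not significant and close the matter. But if 0.055 comes from a subset or from the final-treatment set, the intention-to-treat result could fall on either side of 0.05. The label should wait until the basis of 0.055 is known.

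**The 0.05 threshold is imported.** True, and adopting it now is a choice made after results were seen. The printed labels nevertheless need some stated cut-off.

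**These are secondary results.** True. The primary variable, DSA at 24 months, is untouched, and HbA1c at p=0.013 is below 0.05 as printed. This limits the severity but does not excuse a duplicated table entry.

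**Conclusion.** The concern holds as a reporting defect. On an assumed two-sided 0.05, p=0.055 and p=0.058 do not support the word 'significant', and the printed values do not show a rise. The Group B triglyceride comparison cannot be used as printed. That the entry was copied from diastolic pressure is an inference from the identical figures and the p-values; the true value cannot be recovered from the documents. The missing n is material: the systolic difference of 8 mmHg has p=0.0095 (CI 2.0 to 14.0) with 52 and 53, and p of about 0.055 (CI −0.2 to 16.2) with 29 per arm, both by t test.

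The documents do not show that any printed systolic or HDL p-value is wrong, that there is no systolic difference, or that patients without values differ from those analysed. Severity is at most a should-fix.

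**What to change.** 1. **Systolic pressure.** Identify the n, test and analysis set behind p=0.055. Until then remove 'significantly' and report 133±16 vs 125±15 mmHg, p=0.055, with n per arm, difference and 95% CI. Report the intention-to-treat and final-treatment results whichever side of 0.05 they fall, and let the wording follow the intention-to-treat result.
2. **'Rose'.** In Diabetes and Blood pressure, write *was higher at the end of follow-up* unless change from month 3 is shown. For HbA1c a month-3 value was scheduled: "The HbA1c was measured and a standard oral glucose tolerance test of 75 gr was done at 3, 12 and 24 months". No such schedule is given for blood pressure.
3. **Histology.** Say which comparison each p-value belongs to, and do not call the one with p=0.058 significant.
4. **Triglycerides.** Check the Group B entry against source data and correct it, and the p-value if needed.
5. **Plan and reporting.** State two-sided 0.05 and intention-to-treat as the main set, labelled as fixed after results were known, with secondary p-values exploratory. Give n per arm, test and analysis set for each secondary result, and rejection as count over denominator.

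The cost is wording, one source-data check, and numbers that the sponsor should already hold. No new data collection is needed. The systolic claim may weaken or may be confirmed.

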### **Renal function.**

No significant differences were noted between the groups in creatinine ( $1.34\pm0.4$  vs  $1.4\pm0.4$  mg/dL;  $p=0.458$ ) or proteinuria ( $209\pm185$  vs  $148\pm82$  mg/24h;  $p=0.303$ ) at the end of the follow-up.

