### **Variables:**

#### *Efficacy variables:*

The *primary variable* was the presence of donor-specific anti-HLA antibodies (DSA) at 24 months.

The *secondary variables* were:

- a) Graft and patient survival.
- b) Rate of acute clinical rejection, confirmed by biopsy, calculated glomerular filtration rate (determined by aMDRD) and proteinuria at 3, 6, 12 and 24 months.
- c) BP figures and number of hypertensive patients, lipid levels and need for lipid-lowering drugs, and increase in weight and BMI.
- d) Rate of post-transplant diabetes mellitus (PTDM) or glucose intolerance one year post-transplant according to the criteria of the ADA (PTDM: baseline glycemia  $\geq 126$ , or  $\geq 200$  mg/dl after glucose overload, or need for treatment; glucose intolerance: glycemia after overload of 140-199 mg/dL).
- e) Determination of the lymphocyte subpopulations (CXCR3highCD4+; CCR4highCD4+ and Treg CCR4high) by flow cytometry at 1, 3, 6, 12, 18 and 24 months.
- f) Appearance of acute or chronic pathological lesions of the graft using:

\*Kidney graft biopsy. Biopsies were done before randomization (month 3 post-transplant) and in month 24 post-randomization (protocol biopsies). In the case of suspected acute rejection a biopsy of the graft was done before or within 48 hours of starting anti-rejection treatment. Likewise, a graft biopsy was done at any time if graft dysfunction was detected, as evidenced by proteinuria 0.5 g/day or an increase in the serum creatinine of 25% above its baseline level. The biopsies were evaluated according to the Banff'09 classification (*Sis B, et al Am J Transplant 2010;10: 464-71*). Biopsies done for clinical indication and those done prior to randomization were evaluated locally at each participating center. The local pathologist interpreted the biopsy for the presence of clinical or subclinical rejection, borderline lesions or progression of chronic lesions that

explained a possible graft failure to thus provide the most opportune treatment. The biopsies done and the pre-randomization and final visits were also sent to the pathologist at Carlos Haya Hospital, Malaga, who also interpreted and classified them using the same Banff'09 criteria. The biopsies were processed in each center and sent to the central pathologist for study. The slides comprised at least 2-3 slices of the biopsy. The staining was done locally (hematoxylin eosin, periodic acid Schiff, Masson trichrome and methenamine silver).

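### Several listed renal and metabolic outcomes have no result in the preliminary report, and the only p-value below 0.05 is for HbA1c, which is not a listed outcome

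*Combined protocol and SAP*

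**What the plan says.** Secondary objective 4 asks whether steroid withdrawal brings metabolic and cardiovascular benefit "in terms of renal function, hypertension, diabetes and hyperlipidemia". The *Efficacy variables* list gives three items that bear on it:

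- Item b includes "calculated glomerular filtration rate (determined by aMDRD) and proteinuria at 3, 6, 12 and 24 months".
- Item c is "BP figures and number of hypertensive patients, lipid levels and need for lipid-lowering drugs, and increase in weight and BMI". No visits are stated.
- Item d is "Rate of post-transplant diabetes mellitus (PTDM) or glucose intolerance one year post-transplant according to the criteria of the ADA".

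HbA1c is not in that list. It appears under *Other determinations*: "The HbA1c was measured and a standard oral glucose tolerance test of 75 gr was done at 3, 12 and 24 months".

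The *Statistical Analysis Plan* names the tests (t or Mann-Whitney; chi-square or Fisher). It states no alpha level, no sidedness, no multiplicity rule and no family of tests.

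In the *Preliminary Results*, the *Renal function* section reads "No significant differences were noted between the groups in creatinine", and adds proteinuria at the end of follow-up. The *Diabetes* section gives a non-significant PTDM comparison and then says "the HbA1c values rose significantly" in Group A, with p=0.013. The *Blood pressure* section calls the rise in systolic pressure in Group A significant and prints p=0.055.

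**The concern.** A list of outcomes fixed in the protocol lets a reader judge a significant result against everything that was meant to be looked at. Here part of the list is missing, one listed measure is represented by another that is not listed, and the only p-value below 0.05 belongs to a variable outside the list. A reader of the results sections alone could not tell that HbA1c is a supporting measurement, that the listed glycaemic outcome showed no significant difference, or that planned measures of hypertension, drug need and weight are absent.

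These are secondary outcomes. They are nevertheless the trial's evidence on whether withdrawal brings the benefit that objective 4 asks about.

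**Working it through.** **1. Listed outcomes against reported results**

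| Listed under *Efficacy variables*, items b to d | In the *Preliminary Results* |
|---|---|
| eGFR (aMDRD) at 3, 6, 12, 24 months | Not given; creatinine 1.34 vs 1.4 mg/dL, p=0.458 |
| Proteinuria at 3, 6, 12, 24 months | End of follow-up only, p=0.303 |
| Blood pressure figures | Given: diastolic p=0.715, systolic p=0.055 |
| Number hypertensive | Not given |
| Lipid levels | Given: p=0.677, 0.095, 0.337, 0.469 |
| Need for lipid-lowering drugs | Not given |
| Increase in weight and BMI | Not given |
| PTDM at one year | 25.6% vs 16.7%, p=0.359; no time point of its own |
| Glucose intolerance at one year | Not given |
| HbA1c: not listed | 6.3±1.2% vs 5.7±0.6%, p=0.013 |

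Five rows have no result, if glucose intolerance is counted apart from PTDM. Acute rejection, also in item b, is reported in its own section and serves a different objective.

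**2. Count of tests.** Diabetes 2 + lipids 4 + blood pressure 2 + renal 2 = 10. Taking the conventional two-sided 0.05 (an assumption, since the plan states no level), one of the ten is below it: HbA1c. Systolic pressure at 0.055 is not.

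**3. Can p=0.013 be reproduced?** Not exactly, because numbers analysed are not given. For n per arm, t = (6.3 − 5.7)/√((1.2² + 0.6²)/n) = 0.6/√(1.80/n).

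- With n=33, t = 0.6/0.2335 = 2.57, and p = 0.0125 (equal variance) or 0.0134 (Welch).
- With all 52 and 53 randomized, p = 0.0016 or 0.0018.

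If a t test was used, the printed value fits about 33 per arm. In the same way, systolic p=0.055 fits about 29 per arm; 52 and 53 would give 0.0095. The PTDM percentages also rule out full denominators: 13/52 = 25.0% and 14/52 = 26.9%, not 25.6%; 8/53 = 15.1% and 9/53 = 17.0%, not 16.7%.

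**4. How far HbA1c depends on the choice of family.** Bonferroni-adjusted p = k × 0.013:

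| Tests in family (k) | Adjusted p |
|---|---|
| 2 | 0.026 |
| 3 | 0.039 |
| 4 | 0.052 |
| 10 | 0.13 |

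Holm gives the same 0.13 for ten. The result stays below 0.05 for three tests or fewer. The documents define no family, so this is an illustration only.

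**5. A caution on the ten p-values.** The Group B triglyceride value (76±9.7) is identical to the Group B diastolic pressure. Against 140±54 it does not agree with p=0.469: a t test at 52 and 53 gives p<0.00001. This is probably a copying error. The count above uses p-values as printed.

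**The case against.** The strongest reply is that the section is headed as preliminary, so the missing outcomes may still be coming. Omission is also not confined to metabolic items, since adherence (objective 5) has no result either. This stands as far as intent goes. It does not remove the point, because the same sections already give end-of-follow-up comparisons and describe two of them as significant.

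A reader might infer selective reporting in favour of withdrawal. The documents do not support that. Creatinine is reported as null and is numerically higher in the withdrawal arm (1.4 vs 1.34), so its use in place of eGFR does not favour withdrawal. The *Diabetes* section states the null PTDM result before HbA1c. No section draws an overall conclusion of metabolic benefit.

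A reader might also infer that HbA1c is a chance finding because it fails adjustment. The 0.13 requires pooling renal, lipid, pressure and glycaemic tests, which the plan does not prescribe; the two glycaemic tests alone give 0.026. For ten independent null tests, the chance of at least one p<0.05 is 1 − 0.95^10 = 0.40, and of one at or below 0.013 it is 1 − 0.987^10 = 0.12. Total and LDL cholesterol, systolic and diastolic pressure, and HbA1c and PTDM are unlikely to be independent, and correlation would lower both figures.

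Nor is HbA1c post hoc: it was scheduled at 3, 12 and 24 months, and diabetes is named in objective 4. It is only unlisted as an outcome.

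Two smaller replies also stand. The count of five is a reading, since item d joins PTDM and glucose intolerance and objective 4 does not name weight. The arm differences in mean age (54.8 vs 52.1 years) and sex (75% vs 71.7% male) are small and are not shown to change the creatinine comparison. The case for eGFR rests on the plan having named it.

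**Conclusion.** The point holds as incomplete reporting against the protocol's own list. Five listed measures have no result (counting glucose intolerance separately), and two more lack their planned time points. PTDM, blood pressure figures, lipid levels and proteinuria are reported at least in part, so it would be wrong to say that the planned outcomes as a whole were replaced.

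HbA1c is the only one of ten printed p-values below 0.05, and it is a supporting measurement. The systolic statement at p=0.055 is a second claim of significance, and it does not reach the conventional level. That judgement assumes a two-sided 0.05, because the plan gives none. Whether HbA1c survives adjustment cannot be settled from the documents, because no family is defined.

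The numbers analysed appear smaller than the numbers randomized. The PTDM percentages show this directly; for HbA1c and systolic pressure it rests on assuming a t test.

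**What to change.** - Report every outcome in items b to d by arm, with the number analysed, at the visits the list gives. Item c gives none, so state the visits used.
- Give aMDRD eGFR as the renal outcome at 3, 6, 12 and 24 months, with creatinine as support, and proteinuria at the same visits.
- Give PTDM and glucose intolerance at 12 months. The 24-month glucose tolerance test can be shown as a further time point.
- Label HbA1c as supportive, not a listed outcome, and one of ten unadjusted comparisons. If an adjusted value is shown, state the family and call it a sensitivity illustration.
- Reword the systolic pressure statement so that it does not claim significance at p=0.055.
- Check the triglyceride line against the source data.

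The protocol schedules or lists these measurements, so the work should be mainly re-tabulation, provided that the data were collected as planned. The price in interpretation is a less favourable statement on HbA1c and systolic pressure.
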